Aim 3: Determine the influence of a menthol flavor ban on tobacco purchasing behavior in the context of a reduced nicotine standard using an ETM. At Visit 5, participants will complete two ETMs in the laboratory to model the impact of menthol flavoring and nicotine content on cigarette purchasing in the context of all available tobacco products currently on the market. ETM 1 will evaluate willingness to purchase and smoke non-menthol VLNCs at increasing prices under the scenarios where a

nicotine reduction policy is in effect and menthol is banned in combustible cigarettes. ETM 2 will evaluate willingness to purchase and smoke menthol vs non-menthol VLNCs at increasing prices under the scenario where a nicotine reduction policy is in effect but menthol in combustible cigarettes is available. In both ETMs, all ATPs will be available in different flavors, including menthol, to simulate the real-world marketplace. Hypothesis: In ETM 1, YAs will be more likely to choose an ATP than purchase any cigarettes. In ETM 2, YAs will be more likely to purchase menthol VLNCs or ATPs than purchase non-menthol VLNCs or no tobacco products.

Exploratory Aim: Determine the influence of a menthol flavor ban on tobacco purchase behavior when menthol is banned in all combustible tobacco products (cigarettes, cigars), but is available in non-combustible products (e.g., e-cigarettes).

The proposed research design is unlike existing research, as it combines rigorous, controlled laboratory paradigms of smoking response with “real-world” measurements of the same to determine the relative impact of menthol characteristics and nicotine on cigarette smoking in YAs, a vulnerable group of tobacco users, and adults aged 26-34, who also have high rates of menthol cigarette use. Beyond informing policy, this proposal will validate a new set of measures to be used in future studies to evaluate the potential impact of tobacco policies (e.g., a ban on all flavors) on YA cigarette and alternative tobacco use behavior.

B. Background and Significance

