the products in their account. Real-world brands of each product type will be presented in the ETM and chosen from those with the highest grossing product sales at the time of funding. The ETM tasks will serve as a controlled assessment of tobacco decision-making processes (e.g., alternative product use behavior) to be compared with patterns of product use generated from laboratory and EMA assessment in the field.

Participants can complete the ETMs in person or remotely, online.

The following images of tobacco/nicotine products will be shown in the ETM:

- a) SPECTRUM Study cigarettes menthol OR non-menthol flavors, depending on the ETM;
- b) Little cigars
- c) Cigarillos
- d) E-cigarettes (e.g., cigarette-like systems such as Juul and tank-like systems such as NJOY prefilled tanks)
- e) Snus;
- f) Conventional smokeless tobacco products
- g) Non-prescription medicinal nicotine (e.g., 2mg and 4mg nicotine gum; 7, 14 and 21 mg nicotine patch) menthol and regular flavors
- h) Large Cigars
- i) Hookah/shisha
- j) Tobacco free nicotine pouches

30-DAY FOLLOW-UP

A month (30-days) after the final study visit, participants will complete the smoking stages of change, mFTQ, and ATSQ before completing a third ETM in which will assess appeal for non-menthol VLNCs in the scenario where menthol is restricted in all combustible tobacco products. Thus, the only product in which menthol would be available in ETM 3 is e-cigarettes. After that, participants will complete a brief survey indicating whether smoking and other tobacco use has returned to baseline levels (**End of Study Questionnaire**). This 30-day follow-up will be offered face-to-face or remotely. at the participant's preference. They will also be provided cessation referrals.

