responses on their mobile phone screen. [name] is currently using this EMA platform in her ongoing R01 with YAs, and it has been used it in many prior studies of smoking behavior.^{71,73,74} The selected monitoring schedule was driven by the study aims, and will allow us to capture a random sample of smoking episodes and to characterize variation in smoking reinforcement, craving, and withdrawal within-days and across days.^{147,148} Asking participants to record every smoking episode would be too burdensome and could result in substantial attrition. To ensure we capture smoking episodes for smokers who may be exclusively stimulus-based (e.g., morning only, evening only),¹⁴⁹ we will use an adaptive random prompting schedule that is programmed to coincide with the participant's sleep-wake cycle (e.g., time they wake up, time they go to bed), which will be collected at baseline.

Participants will be able to directly access the EMA survey upon receiving a prompt (vibration or “ping”) to their phone by touching the screen. EMA entries are expected to last ~5 minutes (based on response times in prior studies conducted by the PI),^{111,113} will be date- and time-stamped, and recorded immediately. To enhance compliance, we will provide detailed training on EMA and monetary incentives (see section 2.5. Recruitment and Retention Plan for more detail on monetary incentives). Pre-paid phones or reimbursement for cellular service will be provided (at the participant's choosing). Pre-paid phones will be labeled “government property”. At the 30-day follow-up, participants will complete a brief survey of satisfaction with and reactivity to EMA and another ETM where they will select VLNCs when menthol is banned in all combustible tobacco products, including cigarettes, hookah, little cigars, etc., but not banned in e-cigarettes.

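### The ETM 3 description leaves menthol only in e-cigarettes, which does not follow from the combustible-only menthol ban named in the Exploratory Aim and in ETM 3's own scenario

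*Combined protocol and SAP*

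**What the plan says.** All references are to the combined protocol and SAP.

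- **Section A, Exploratory Aim.** The question is purchasing behavior when "menthol is banned in all combustible tobacco products (cigarettes, cigars), but is available in non-combustible products (e.g., e-cigarettes". The exemption is given for a class of products, with e-cigarettes as one instance.
- **30-Day Follow-Up, scenario.** ETM 3 assesses appeal of non-menthol VLNCs "in the scenario where menthol is restricted in all combustible tobacco products". This matches the aim.
- **30-Day Follow-Up, next sentence.** "Thus, the only product in which menthol would be available in ETM 3 is e-cigarettes".
- **Section C.5, EMA Procedure.** A second description of ETM 3 says that "menthol is banned in all combustible tobacco products, including cigarettes, hookah, little cigars, etc., but not banned in e-cigarettes". It does not say what happens to other non-combustible products.
- **Section C.6, product list, just before the 30-Day Follow-Up.** Besides e-cigarettes the list includes snus, "Conventional smokeless tobacco products", medicinal nicotine (ending "7, 14 and 21 mg nicotine patch) menthol and regular flavors") and "Tobacco free nicotine pouches".
- **Section A, Aim 3, and section C.6.** In ETM 1 and ETM 2 every alternative product is offered in several flavors, menthol among them.

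**The concern.** ETM 3 is the only task that serves the Exploratory Aim, so its menu decides which policy the aim can speak to. The sentence on e-cigarettes is worded as a deduction from a combustible-only restriction, but a restriction of that kind leaves snus, smokeless tobacco, medicinal nicotine and pouches untouched. No section gives a reason for taking menthol out of them.

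Two things are at stake if the menu follows that sentence. First, participants could not move to a menthol pouch, snus, smokeless or medicinal nicotine product, so the task could not show that form of substitution even though the aim covers non-combustible products. Second, e-cigarettes would be the sole remaining source of menthol for a sample required to smoke menthol at least 80% of the time (section F). More e-cigarette purchasing could then reflect the combustible ban, the loss of menthol elsewhere, or both, and the task could not separate them. The study is intended to inform regulation of menthol, so the scenario tested should be the one named.

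**Working it through.** No sample size, power or error-rate figure enters this point, and the plan gives no figure to reproduce. The check is a comparison of texts and a count of the product list in section C.6.

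**1. Classify the list (items a to j).** Item a is the study cigarette. Items b to j are nine alternative classes.

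- Combustible: little cigars, cigarillos, large cigars, hookah = 4. The Exploratory Aim and section C.5 themselves treat cigars, little cigars and hookah as combustible.
- Non-combustible: e-cigarettes, snus, conventional smokeless, medicinal nicotine, nicotine pouches = 5. The documents do not label each of these; the classification rests on the nature of the product.
- Check: 4 + 5 = 9.

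**2. Count the alternative classes in which menthol may be sold.**

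| Scenario | Combustible (of 4) | Non-combustible (of 5) | Total (of 9) |
|---|---|---|---|
| ETM 1 and ETM 2 (section C.6) | 4 | 5 | 9 |
| Exploratory Aim, read as a class | 0 | 5 | 5 |
| ETM 3, e-cigarette sentence | 0 | 1 | 1 |
| ETM 3, section C.5 | 0 | at least 1; other 4 not stated | not determined |

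**3. Size of the conflict.** Aim minus e-cigarette sentence: 5 − 1 = 4 classes, or 4/5 of the non-combustible classes.

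**4. What would change from ETM 1 to ETM 3.** ETM 1 already removes menthol from cigarettes.

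- Under the aim, ETM 3 would further remove it from 9 − 5 = 4 classes, all combustible.
- Under the e-cigarette sentence it would remove it from 9 − 1 = 8 classes, of which 4 are combustible and 4 are not.
- So 4/8, half of the removals, would lie outside the stated ban.

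These are counts of list entries. They do not measure purchasing, and the documents give no figure for how often participants would choose menthol in the four classes.

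**5. Does another section settle it?** No. Section C.5 is compatible with either menu. Section J.4 (ETM Analyses) names no analysis specific to ETM 3, and section J.5 lists flavor preference by product type as an exploratory ETM outcome without saying which ETM supplies it.

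**The case against.** The strongest reply is that this is one loosely drafted sentence. The sentence before it, the Exploratory Aim and section C.5 all describe a ban in combustibles, and no section sets out the ETM 3 menu product by product. The programmed task may well carry menthol in all non-combustible classes. That stands as far as it goes: a reader might infer that ETM 3 has been misconfigured, or that records exist from a wrong menu, and the documents establish neither. What remains is that they do not say which menu participants see, and the only explicit statement contradicts the aim.

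An e-cigarette-only exemption may also be what the investigators want, since both ETM 3 descriptions single out e-cigarettes. That is possible, but the aim would then need different wording. Conversely, the aim does not say that all five classes keep menthol. It refers to non-combustible products with an example; the class reading is the natural one, but it is a reading.

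A reader might further infer that switching to e-cigarettes will be overstated against ETM 1. That direction is plausible if the menu is e-cigarette-only, but it is not shown. The plan specifies no comparison of ETM 3 with ETM 1. Such a comparison would differ in other ways too: ETM 3 comes 30 days after Visit 5, is not counterbalanced with the other two tasks, and has no stated abstinence requirement, whereas Visit 5 calls for more than 12 hours.

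Finally, the reach is limited. Aim 3 uses ETM 1 and ETM 2, which the sentence does not touch, and purchases are hypothetical.

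**Conclusion.** The inconsistency is real and lies on the face of the text, both between the Exploratory Aim and the 30-Day Follow-Up section and between two adjacent sentences of the latter. If ETM 3 is built as the e-cigarette sentence says, it models a combustible menthol ban plus removal of menthol from four of five non-combustible classes. It could not then show substitution to those menthol products, nor attribute a shift to e-cigarettes to the combustible ban alone. Such a shift may be inflated, by an amount that cannot be estimated from the documents.

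This rests on two assumptions: that the aim's exemption covers non-combustible products as a class, and that snus, smokeless tobacco, medicinal nicotine and pouches belong to it. Whether the task as programmed has the problem is not known. The consequence is confined to the Exploratory Aim, and the change should be made because it decides what that aim can answer.

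**What to change.** Add to the 30-Day Follow-Up section a short table stating, for each product class on the ETM list, whether menthol is offered in ETM 3. Make the Exploratory Aim, the 30-Day Follow-Up text and section C.5 agree with it, by one of two routes:

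1. Keep menthol in the non-combustible classes that carry it in ETM 1 and ETM 2, consistent with the aim's wording, and delete the e-cigarette-only sentence.
2. If an e-cigarette-only exemption is intended, rewrite the Exploratory Aim to name that policy, and limit its conclusion to it.

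If the programmed menu already matches the chosen route, the cost is a text edit. If it does not, the marketplace settings must also change. Should that happen after any ETM 3 data have been collected, each record needs a menu-version indicator so that the two menus are not pooled unknowingly; that is the one small downside.

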Following a telephone screen, potentially eligible participants will attend a pre-screen/baseline session either in-person or remotely to confirm eligibility. After completing informed consent, participants will verify age, participants will be asked when they smoked their last cigarette, a baseline carbon monoxide measurement will be taken, and female participants will be asked to verify negative pregnancy status. Participants will then complete a medical history questionnaire, and asked about intentions to quit smoking, mental health with the **Patient Health Questionnaire-9**, and suicide risk using the **MINI Suicide screening** before eligibility can be confirmed. Eligibility determination will be made by the RA based on the inclusion/exclusion criteria. If the participant is deemed initially eligible, the Baseline session will immediately begin. Eligibility criteria will be reviewed by the PI (and the medical monitor, if necessary), to confirm final eligibility for the study, prior to Visit 2. If the participant is eligible after Visit 1 screening procedures, the first baseline session will begin immediately. Participants who are ineligible will be paid \$25 and will not complete the baseline procedures. The RA will make the initial determination of eligibility; final eligibility will be confirmed by the PI (and medical monitor if necessary), prior to Visit 2. Eligible participants will move on to complete the baseline surveys, which is a battery of questionnaires assessing baseline characteristics. After these assessments, the EMA application will be loaded onto the participant's phone or a study-provided phone (at their choosing) and participants will be given a 10-15 minute training, as per the PIs previous EMA studies, on how to use the EMA platform. For 7-days following V1, participants will smoke their usual brand cigarette in their home environment, as per usual, and measurements of cigarettes per day, craving, symptoms of nicotine withdrawal, subjective response, and alternative tobacco use will be assessed twice daily via EMA.

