At the end of V2, participants will receive the first set of assigned research cigarettes and will be asked to smoke those cigarettes in their home environment for 7 days; starting on the day after V2. The ordering of flavor of the research VLNCs to be smoked (menthol and non-menthol) will be counterbalanced and assigned prior to Visit 2 (Individuals who complete the session remotely will be scheduled for a pick-up date to get the VLNCs1). During each 7-day period of exposure, participants will be instructed to switch their usual brand cigarette for the assigned research cigarette and will provide daily data on smoking quantity, craving, withdrawal, subjective response, and alternative tobacco product use via twice daily EMA surveys. We will allow for other tobacco product use without specific instruction to align with the real-world scenario, as these products will exist on the market even if a menthol ban and/or a reduced nicotine standard are enacted. Given the high prevalence of dual and poly-tobacco use in this age group, we will examine change in alternative tobacco product use between conditions as a secondary outcome in exploratory analyses, per Co-I [name]'s and [name]'s previous work. Participants will have a 7-day period wash-out period of return to smoking as usual (own brand of cigarette) between the experimental conditions.

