Smoking Sessions 2 and 3 (Visits 3 and 4): Research Cigarettes. Study Visits 3 and 4 (V3-V4) will be identical to each other. Participants will return to the laboratory for V3 and V4 at the end of each 7-day period of using the assigned research cigarette in their home environment, and smoke that assigned research cigarette in the laboratory. At each visit, participants will be asked to abstain from cigarette smoking or other nicotine for > 12 hours (verified by expired CO \leq 6ppm or >50% reduction in CO from baseline, per [name] research. Additionally, prior to smoking participants will be asked when they smoked their last cigarette).²⁴ Before smoking the assigned research cigarette, participants will complete a **cigarette purchase task (CPT)**, a behavioral economics-based measure of cigarette reinforcement, which assesses hypothetical demand for cigarettes across a range of prices, and a **cross-price elasticity purchase task**, which assesses hypothetical demand for experimental cigarettes at increasing prices of an individual's preferred brand of cigarettes. Participants will also complete a **perceived health risk survey** for the study cigarettes, a **predicted behavior questionnaire**, an **expected utility questionnaire**, the **American**

Thoracic Society Questionnaire, and heart rate and blood pressure will be taken before smoking. They will smoke one assigned research cigarette ad libitum at each visit. Puff topography, subjective response, heart rate and blood pressure, and CO boost will be collected. After smoking, participants will complete the **Modified Cigarette Evaluation Questionnaire (mCEQ¹³⁸⁻¹⁴⁰)**, the **Nicotine Drug Effects Questionnaire (N-DEQ)**, the **Duke Sensory Questionnaire (DSQ)**, and the **Minnesota Nicotine Withdrawal Scale (MNWS)**. At the conclusion of visit 4, participants will be asked to participate in a brief assessment to query about satisfaction with and reactivity to the daily EMA survey (**post-lab and post-EMA reactivity questionnaire**).

EXPERIMENTAL TOBACCO MARKETPLACE (ETM)

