C.4.e. Research Cigarette Compliance. Co-I's [name] and [name], and Consultant [name] all have extensive experience measuring and analyzing the impact of noncompliance with research cigarettes in similar trials,^{26,144} and their expertise will help ensure that non-compliance is mitigated and controlled to the best extent possible using the following methods. (1) Compliance with research cigarettes has been demonstrated to increase when incentives are provided for using them. This incentive will be a payment made at each in-person session. To reduce distribution, hoarding, and/or overconsumption, participants will also receive a nominal payment for returning unused cigarettes (\$0.25/cigarette up to \$20 maximum per participant). Participants will be instructed to return all unused cigarettes and empty cigarette packs to the laboratory each week. At each study visit, participants will also be asked to bring all used study and non-study cigarette butts that they have smoked for the past 7 days. They will be given

plastic bags labeled with their study ID number and calendar dates; a single plastic bag will be used to collect the butts for a single day. The payment schedule for returning research cigarettes (smoked or unsmoked) at each in-person visit (in the form of used butts) is as follows: 75-100%, \$7; 50-74% returned, \$5; 25-49% returned, \$2.50; and 0-24% returned, \$0. Participants can receive \$1 for each returned empty pack, up to \$5 maximum. The team has used this strategy to incentivize product accountability in other studies with success. Honesty of reporting will also be encouraged throughout the study. We will examine concordance between EMA reports of cigarettes per day and number of cigarettes returned to verify compliance. (2) Unfortunately, as participants' usual brand cigarettes will exist in the real world, noncompliance can be an issue in all such studies of this kind.¹⁴⁵ However, noncompliance can be used as an index of dissatisfaction with reduced-nicotine cigarettes.¹⁴⁶ Differences in noncompliance across research cigarette conditions will be examined in exploratory analyses in an effort to inform the application of a reduced nicotine product standard and a menthol cigarette ban to age groups that prefer menthol cigarettes.

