C.4.f. Research Cigarette Distribution and Accountability. Participants will be given enough cigarettes to accommodate usual smoking patterns until the next visit in 7 days (125% of their baseline cigarettes per day, based on the team's previous work). At V2, participants will report the number of cigarettes smoked per day. Based on this number, staff will calculate the number of SPECTRUM cigarettes needed to provide the participant for each 7-day experimental period (# of own cigs smoked per day x 125% x 7 days). At each in-person visit, research staff will complete a 'Product Accountability Log' with participants to record used and unused cigarettes. Any discrepancies in the product dispensed versus product returned will be discussed and recorded in the log. Participants will be surveyed about desire to quit smoking at each in-person visit. If they endorse that they wish to quit, they will be asked if they still want to receive research cigarettes. If they do not, no study cigarettes will be dispensed and the participant will be retained in the study with no penalty and will continue to complete all subsequent EMAs, the ETM, and the 30-day follow-up. Changes in desire to quit and actual quitting behavior will be examined as an outcome in exploratory analyses, where sample size allows. In her ongoing R01, Co-I [name] dispenses research cigarettes in this manner to 15-19-year-old daily smokers with approvals from the FDA and her institutional IRB.

Measures Descriptions

Participants will complete validated measures from the PhenX Toolkit and the team members' published studies. The following domains will be assessed in the baseline survey: (1) demographics; (2) Tobacco use patterns (age at first use; nicotine dependence (time-to-first use and mFTQ),¹⁴⁵⁻¹⁴⁶ cigarettes per day; alternative tobacco product use; motivation to quit and quit history; peer tobacco use; tobacco marketing/media exposure¹³³⁻¹³⁶; and weekly tobacco expenditure; (3) Self-reported appeal of menthol cigarettes; (4) Harm perceptions of

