Primary Outcomes: (a) The relative reinforcing value (RRV) of usual brand cigarettes vs menthol VLNCs; (b) RRV of non-menthol VLNCs vs menthol VLNCs. RRV will be operationalized as within-subject differences in subjective ratings of cigarette appeal/reinforcement (satisfaction, reward, craving reduction, physical sensations) during each ad libitum smoking session. Secondary Outcomes: (a) CO boost; and (b) puff topography (number of menthol versus non-menthol cigarette puffs consumed, number of minutes smoked, interval between puffs).

Analysis of covariance will be conducted to examine effects of cigarette type (usual brand, menthol VLNC, non-menthol VLNC) on the outcomes of interest, controlling for cigarettes per day (CPD), nicotine dependence, race/ethnicity, gender, and age of smoking onset as potential covariates. Factors related to study drop-out and differences in cigarette compliance will also be examined as potential covariates. Exploratory analyses will examine differential reactions to usual brand and each research cigarette by race/ethnicity (White, Black, Hispanic, Other) and by gender. Significant interactions will be followed up with individual contrasts of cell means using Fisher's Least Significant Difference tests. We will examine whether topography differs as a function of in-person versus remote session.

3. EMA Analyses (Aim 2)

Primary Outcomes: (a) within-day subjective response (craving reduction, satisfaction, psychological reward, physical sensations like throat grab) to the most recent cigarette smoked; (b) within-day number of research cigarettes smoked per day; (c) within-day number of non-research cigarettes smoked; and (d) within-day withdrawal intensity. Secondary Outcomes: (a) within-day use of alternative tobacco products; (b) changes over the course of days (creating an average change score for each person) for each outcome; (c) number of days abstinent from tobacco use.

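### Research-cigarette compliance, which arises after flavour assignment, is a candidate covariate in the primary Aim 1 model; scored per condition, it could change what the menthol contrast estimates

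*Combined protocol and SAP*

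**What the plan says.** Section J.2 (Laboratory Analyses, Aim 1) makes the within-person rating difference between non-menthol and menthol VLNCs primary outcome (b). It plans an analysis of covariance across three cigarette types: usual brand, menthol VLNC and non-menthol VLNC. After naming the baseline covariates it states: "Factors related to study drop-out and differences in cigarette compliance will also be examined as potential covariates". It gives no rule for entry and no scoring rule, and it does not say that the model without compliance stays primary.

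The timing comes from the visit descriptions:

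- Flavour order is fixed before Visit 2 (Smoking Session 1).
- "At the end of V2, participants will receive the first set of assigned research cigarettes" (same section).
- "Participants will return to the laboratory for V3 and V4 at the end of each 7-day period of using the assigned research cigarette" (Smoking Sessions 2 and 3). The laboratory rating is taken at those visits.

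Section C.4.e describes how compliance is checked: "We will examine concordance between EMA reports of cigarettes per day and number of cigarettes returned to verify compliance". It also says that "noncompliance can be used as an index of dissatisfaction with reduced-nicotine cigarettes", and that "Differences in noncompliance across research cigarette conditions will be examined in exploratory analyses". The Aim 2 text in Section A likewise lists cigarette compliance among the things to be compared between menthol and non-menthol VLNCs.

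**The concern.** Compliance sits between the assigned flavour and the rating, and the plan itself asks whether flavour changes it. A variable in that position is not an ordinary covariate. Adjusting for it can remove part of the flavour effect, or add a spurious component if compliance and ratings share an unmeasured cause. The same behaviour would then be an outcome in one part of the plan and an adjustment variable in another.

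At stake is the contrast that the background section intends to inform regulation of menthol. As written, two analysts could both follow J.2 and report different values of primary outcome (b) from the same data, one adjusted for compliance and one not.

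**Working it through.** No figure in the plan bears directly on this point. Section J.1 states power of 0.8 at 100 participants but gives no effect size, SD or within-person correlation, and nothing in the documents gives the effect of flavour on compliance. The check is therefore on order of events and algebra; every number put into the formulas is an assumption.

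**1. Order of events.** Flavour order assigned (before V2), first research cigarettes dispensed (end of V2), compliance accrues (each 7-day period), rating taken (V3 or V4). Compliance follows assignment and precedes the outcome in both VLNC conditions.

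**2. Usual-brand level.** The week before V2 is described thus: "For 7-days following V1, participants will smoke their usual brand cigarette in their home environment, as per usual" (Pre-Screening/Baseline Session). No research cigarette has been dispensed by then, so a per-condition research-cigarette compliance score does not exist for that level of cigarette type. It cannot enter the three-type model without an invented value or the loss of that level.

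**3. Effect of per-condition adjustment.** For complete pairs, let dR and dC be the mean menthol-minus-non-menthol differences in rating and compliance, each in SDs of the within-person difference, and r the correlation of those two differences. With subject effects, the model reduces to regressing the rating difference on the compliance difference. The flavour coefficient is the intercept:

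adjusted contrast = dR − r × dC

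Assuming dR = 0.30:

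| r | dC = +0.30 | dC = 0 | dC = −0.30 |
|---|---|---|---|
| 0.2 | 0.24 | 0.30 | 0.36 |
| 0.3 | 0.21 | 0.30 | 0.39 |
| 0.5 | 0.15 | 0.30 | 0.45 |

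For example, 0.30 − 0.3 × 0.30 = 0.21. A simulation of 400,000 pairs gave 0.209 for that cell, 0.150 for r = 0.5 with dC = +0.30, and 0.389 for r = 0.3 with dC = −0.30.

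**4. Effect of a person-level mean.** The score is the same in both conditions, so it cancels from the within-person difference and the contrast stays at dR. The simulation gave 0.299 at r = 0.3, dC = +0.30.

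**5. No true flavour effect.** Assume a total effect of 0, menthol raising compliance by 0.4 SD, and an unmeasured cause with loading 0.5 on both compliance and rating, so that the slope is 0.5 × 0.5 = 0.25. The per-condition estimate is then 0 − 0.25 × 0.4 = −0.10. In 8,000 simulated trials of 100 participants, the compliance-adjusted test rejected 10.7% of the time, against 4.9% unadjusted.

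These runs confirm the mechanism. They say nothing about the values of dC or r in this trial.

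**The case against.** The strongest reply is that harm needs several things at once. Compliance must actually be entered, since J.2 calls it only a potential covariate; it must be scored per condition; flavour must shift it; and it must be related to the rating. The other covariates in J.2 are person-level, and a per-condition score does not fit the three-type model as specified, so a person-level reading is plausible and would leave the contrast intact. All of this stands, and it is why the point is conditional. It does not settle the matter: J.2 does not choose a score, and its reference to differences in compliance resembles the between-condition comparison in C.4.e.

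A second reply is that J.2 has no entry rule for its baseline covariates either. That is true, and the fix here does not cure it. But a person-level baseline covariate, entered as a main effect in complete pairs, cancels from the within-person contrast; per-condition compliance does not. Similarly, a covariate entered uncentred with a cigarette-type interaction moves the type coefficient whatever the covariate is. That is a coding matter, not an argument against compliance in particular.

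A reader might infer from C.4.e that better compliance with menthol is expected, so that adjustment would shrink the menthol effect. The documents do not support this. The dissatisfaction remark concerns reduced-nicotine cigarettes as a class, which includes both study cigarettes, and no direction is stated for flavour.

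**Conclusion.** The point holds as a conditional fault in the primary Aim 1 analysis. The plan admits a post-assignment variable, which it also studies as a possible consequence of flavour, to the candidate covariates of the primary model, and nothing confines that adjustment to a sensitivity role. If compliance is entered per condition and flavour shifts it, primary outcome (b) ceases to be the total flavour effect. A person-level mean in complete pairs does no such harm, and there is no shift if dC = 0.

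Direction and size are unknown. The 0.15 to 0.45 range around 0.30 rests wholly on assumed dR, dC and r. A reader might conclude that the primary contrast will be biased; the documents support only that it may be, because entry is optional and scoring is unstated. The change should be made, since it is cheap and the ambiguity affects a primary outcome.

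**What to change.** In J.2, delete differences in cigarette compliance from the candidate covariates of the primary model. Restrict that model to covariates measured before the first research cigarette is dispensed: cigarettes per day, dependence, race/ethnicity, gender, age of smoking onset and baseline predictors of drop-out. For cigarettes per day, either the baseline survey value or the one in C.4.f ("At V2, participants will report the number of cigarettes smoked per day") meets this condition; the plan need only name which.

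Keep compliance as an outcome compared between the two VLNC conditions, as already planned. Label any compliance-adjusted Aim 1 model a sensitivity or mediation analysis, limit it to the two VLNC conditions, and state how compliance is scored.

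The cost is wording only, with no new data. The one thing given up is primary status for a compliance-adjusted result.
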